- Unwilling to abstain during the study from using smoking cessation aids other than those provided by the study;
- Experienced a prior adverse drug reaction to varenicline;
- Report an unstable medical condition, epilepsy, or severe renal impairment;
- Had an inpatient psychiatric hospitalization and/or serious suicidal ideation or suicide attempt in the prior six months;
- Have active problem substance use (other than nicotine) severe enough to compromise ability to safely participate in the study protocol.
- Evidence of active problem substance use severe enough to compromise ability to safely participate, in the investigator's opinion;

- Unwilling to provide urine samples;
- Any condition or situation that would, in the investigator's opinion, make it unlikely that the participant could adhere safely to the study protocol;
- Ward of the state.

Randomization

Eligible participants will be randomly assigned in a 1:1:1 ratio, in blocks of 6, to V+BC (varenicline and behavioral counseling), P+BC (identical appearing placebo and behavioral counseling), or EUC (enhanced usual care). Randomization will be stratified by secondary or post-secondary school status. The randomization scheme will be computer generated by the Massachusetts General Hospital (MGH) Research Pharmacy by personnel with no other interactions with study staff or participants. Randomization codes will be held in the research pharmacy and made available to study investigators only in the case of urgent medical need. There will be separate randomization codes for apo-varenicline, imported from Canada under a provisional FDA allowance, and domestic generic varenicline will full FDA approval. Treatment will be assigned according to study number, assigned sequentially to eligible participants who enroll in the trial and attend the baseline visit.

Masking/Blinding

Outcome assessors, data managers, and analysts will be blinded to treatment assignments. All study staff and participants will be blind to study medication assignment for the primary outcome comparing V+BC and P+BC. Interventionists and their clinical supervisors will be unblinded to assignment to behavioral counseling and will not be involved in assessments, data management, or data analysis.

Analytic Approach

Primary Outcome

The primary outcome for the study will be...

1. Cotinine-verified self-reported nicotine vaping abstinence from week 9 to week 12 of the study.

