 - a. [Time frame] Self-reported abstinence and urine or saliva samples will be collected during (a) the baseline visit, (b) every week from weeks 1 to 12 during the randomization interval, and (c) at weeks 16, 20, and 24 during the follow-up interval. The primary outcome will then consist of continuous abstinence status over weeks 9, 10, 11, and 12 for each participant converted to a binary value (1 = abstinent across all 4 study visits, 0 = non-abstinent for at least one of the 4 study visits).
 - b. [Biochemical verification] Self-reported nicotine vaping abstinence will be considered verified given a semi-quantitative cotinine of less than 30ng/ml. For virtual sessions, participants will provide the sample during the videoconferencing session and will show results to the assessor. Those who report no vaping use since the last study visit but who have a cotinine of 30ng/ml or higher will be considered non-abstinent. Those who are missing cotinine values but self-report vaping will be considered non-abstinent.
 - c. [Self-reported abstinence] Self-reported vaping will be assessed at all visits using the timeline follow-back (TLFB; Robinson, Sobell, Sobell, & Leo, 2014). The recall period will be 60 days at enrollment and for all subsequent visits will be the interval between the prior and current visit.
 - d. [Randomization groups] The primary analysis will focus on V+BC and P+BC groups.

Covariates

We will use, at a minimum, 2 covariates in our analysis and missing data imputation:

- Biological sex at birth (male [referent] versus female).
- Summed scores from the ECDI (Foulds et al., 2015), a 10-item inventory with scores ranging from 0 – 20 (higher scores indicating greater E-cigarette dependence).

All covariates will be collected during the baseline visit.

Missing Data

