Missing abstinence data for any of the study weeks 9, 10, 11, or 12 will be imputed 40 times using multiple imputation via chained equations (MICE; Azur, Stuart, Frangakis, & Leaf, 2011). Abstinence status will be imputed all non-missing time points and using the set of 2 covariates collected at the baseline visit described above. Imputation will be done via fully conditional specification with predictive mean matching using logistic regression. Following each imputation iteration, the 4 observed and/or imputed values per participant across the 4 study visits will be converted into the final binary outcome via the rules given above. For instances in which a participant only partially completed the baseline ECDI, missing responses to individual questions will be singularly imputed via an item response theory model fit to all non-missing responses: a binomial regression with population-level effects for items and a participant-varying intercept term.

Statistical Model and Tests

We will use a logistic regression model to assess continuous cotinine-verified self-reported abstinence across study weeks 9 – 12 for participants in the V+BC and P+BC arms (We will exclude participants in the EUC arm). Missing data will be imputed per the method specified above. We will then apply our logistic regression model to each set of observed and imputed data, and pool the regression estimates according to Rubin's rule.

Our primary test of interest will be a dummy-coded contrast comparing the P+BC group (coded as 0) to the V+BC group (coded as 1). Statistical significance for the contrast between varenicline and placebo will be determined using a z-test applied to the pooled mean estimate divided by the pooled standard error. We hypothesize that those assigned to V+BC will have significantly higher abstinence rates compared to those assigned to P+BC, which will be confirmed with $p < 0.05$ and an odds ratio greater than one.

The logistic regression model will include the 2 covariates assessed at baseline (biological sex and summed scores for the ECDI). Covariates will be standardized (mean-centered and scaled by the standard deviation). The analysis will be intent-to-treat; all subjects randomized at the beginning of the study will be included in the analysis, irrespective of whether they receive their assigned behavioral treatment or take their assigned medication.

Secondary Outcomes

The secondary outcomes for the study will be...

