Missing abstinence data for any of the study weeks 9, 10, 11, 12, 16, 20, or 24 will be imputed 40 times using MICE via the same approach and covariates described for the primary outcome. Following each imputation iteration, for continuous abstinence over weeks 9 – 24, the 7 observed and/or imputed values per participant across the 7 study visits will be converted into the final binary outcome via the rules given above.

Inventory Measures

Missing summed scores for the MNWS, QVC, and the MASQ-D30 for any of the study weeks 1 – 24 will be imputed 40 times using MICE. Summed scores will be imputed using the set of 2 baseline covariates described above, as well as a participant's baseline summed score for the given inventory measure. Imputation will be done via fully conditional specification with predictive mean matching using linear regression.

Statistical Models and Tests

We will conduct 5 secondary analyses total for the 3 vaping abstinence outcomes, 3 secondary analyses and 3 exploratory analyses total for the 3 inventory measures, and a secondary analysis for adverse events.

Biochemically-Verified Vaping Abstinence

We will use a logistic regression model to assess (1) continuous vaping abstinence across study weeks 9 – 12, (2) continuous vaping abstinence across study weeks 9 – 24, and (3) 7-day point-prevalence cotinine-verified self-reported abstinence at week 12. Missing data will be imputed per the method specified above. We will then apply our logistic regression model to each set of observed and imputed data, and pool the regression estimates according to Rubin's rule.

The logistic regression model will include the 2 covariates assessed at baseline (biological sex and summed scores for the ECDI). Covariates will be standardized (mean-centered and scaled by the standard deviation). The analysis will be intent-to-treat; all subjects randomized at the beginning of the study will be included in the analysis, irrespective of whether they receive their assigned behavioral treatment or take their assigned medication.

We will conduct two types of analyses:

1. We will assess a single dummy-coded contrast comparing the P+BC group (coded as 0) to the V+BC group (coded as 1), excluding participants in the EUC group. Statistical significance will be determined using a z-test applied to the pooled mean estimate divided by the pooled standard error. We will conduct this analysis for our two secondary vaping abstinence outcomes.

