2. We will assess a pair of dummy-coded contrasts comparing the EUC group (coded as 0) against (1) the V+BC group (coded as 1) and (2) the P+BC group (coded as 1). Statistical significance will be determined via an analysis of variance comparing a simpler null model (with contrasts for V+BC and P+BC fixed to zero) against the more complex model with both contrasts freely estimated. If the Wald test for the model comparison is significant, we will conduct post-hoc tests assessing the 3 possible comparisons between groups (EUC vs. P+BC, EUC vs. V+BC, and P+BC vs. V+BC). We will conduct this analysis for our primary vaping abstinence outcome as well as our two secondary vaping abstinence outcomes.

Table 1 summarizes all secondary analyses for the vaping abstinence outcomes. Tests will be deemed statistically significant for $p < 0.05$ following a correction using the Benjamini-Hochberg method across the 5 analyses.

Table 1: Secondary analyses for vaping abstinence outcomes

Vaping abstinence outcome	Contrast
Continuous abstinence (over weeks 9 – 12)	Omnibus test for EUC vs. V+BC, EUC vs. P+BC, and P+BC vs. V+BC
Continuous abstinence (over weeks 9 – 24)	Contrast of P+BC vs. V+BC (No EUC)
Point-prevalence abstinence (week 12)	Omnibus test for EUC vs. V+BC, EUC vs. P+BC, and P+BC vs. V+BC

Inventory Measures

We will use a linear regression model to assess the post-baseline summed scores collected over weeks 1 – 12 (at weekly or monthly intervals) for (1) the MNWS, (2) the QVC, and (3) the MASQ-D30. The linear model will be estimated using generalized estimating equations (GEE; Liang & Zeger, 1986),

providing estimates and standard errors robust to violations of distributional assumptions (e.g., normality) and heteroscedasticity.

The linear regression model will include covariates for (a) biological sex and baseline summed scores for the ECDI (see above), (b) a participant's baseline score on the given inventory measure, and (c) linear and quadratic time trend terms using number of days since the baseline visit. Covariates will be standardized (mean-centered and scaled by the standard deviation). The analysis will be intent-to-treat; all subjects randomized at the beginning of the study will be included in the analysis, irrespective of whether they receive their assigned behavioral treatment or take their assigned medication.

We will conduct two types of analyses:

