1. We will test whether our conclusion on efficacy is robust to the inclusion/exclusion of the two covariates (biological sex and nicotine dependence severity). We will rerun analyses excluding these covariates and see if conclusions change.
2. We will test whether our conclusion on efficacy is robust to the approach for imputation of missing data. We will (a) rerun the adjusted (i.e., with covariates) models on the observed data only and (b) rerun the adjusted models on a dataset with the observed data and all missing outcome data imputed as non-abstinent.
3. We will conduct a per protocol analysis by evaluating results among participants who use varenicline on most days in the trial (e.g., > 50 or 75%).

Power

Sample size was determined based on the assumption that use of varenicline for vaping cessation in adolescents would require an effect that at least doubled cessation rates over placebo to be worth the risks inherent in use of pharmacotherapy. Abstinence rates of 24% have been reported with TIQ alone in adolescents who vaped and were not necessarily dependent (Graham, Jacobs, & Amato, 2020; Graham, Amato, Cha, Jacobs, Bottcher, & Papandonatos, 2021). In this trial, requiring nicotine dependence to enroll, we postulate that addition of varenicline to behavioral counseling and TIQ will double abstinence rates. A sample size of 100 per arm, with 80 analyzable per arm, would yield power of 0.88 with a two-sided alpha of 0.05 with abstinence rates of 25% in the P+BC arm and 50% in the V+BC arm.

Software and Data Management

All analyses will be done using the statistical software R (version 4.1.1; R Core Team, 2021) and integrated development environment RStudio (version 2020.9.0.351; RStudio Team, 2021). Data will be prepared using the R packages ‘dplyr’ (version 1.0.7; Wickham, François, Henry, & Müller, 2021) and ‘tidyr’ (version 1.1.4; Wickham, 2021). Models will be fit using the R package ‘geepack’ (version 1.3-2; Højsgaard, Halekoh, & Yan, 2006). Missing data will be imputed using the R package ‘mice’ (version 3.13.0; Van Buuren & Groothuis-Oudshoorn, 2011). Reproducible code and de-identified data will be organized using the R package ‘targets’ (version 0.8.1; Landau, 2021).

References

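### Randomization is stratified by school status, but no specified model or imputation includes it; the cost is a slightly conservative primary test and a little lost power if school status predicts abstinence.

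*SAP*

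**What the plan says.** SAP, Randomization: "Randomization will be stratified by secondary or post-secondary school status". School status is not mentioned again in the document.

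The covariates are set out as follows.

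- **Primary Outcome, Covariates:** "We will use, at a minimum, 2 covariates in our analysis and missing data imputation". The two named are sex and the ECDI score.
- **Primary Outcome, Statistical Model and Tests:** "The logistic regression model will include the 2 covariates assessed at baseline (biological sex and summed scores for the ECDI"). The secondary abstinence models repeat this.
- **Primary Outcome, Missing Data:** missing abstinence is imputed from the non-missing time points, "using the set of 2 covariates collected at the baseline visit described above".
- **Secondary Outcomes, Missing Data:** abstinence is imputed "using MICE via the same approach and covariates described for the primary outcome". For the inventories, "Summed scores will be imputed using the set of 2 baseline covariates described above", together with the baseline score of that inventory.
- **Statistical Models and Tests, Inventory Measures:** "The linear regression model will include covariates for (a) biological sex and baseline summed scores for the ECDI", plus the baseline inventory score and linear and quadratic time terms.
- **Adverse events:** unstratified Fisher's exact tests.
- **Sensitivity Analyses:** the covariate check only takes sex and ECDI out: "We will rerun analyses excluding these covariates and see if conclusions change". Nothing is added.

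**The concern.** Stratified blocks force the arms to be nearly equal on school status. If school status is related to abstinence, the treatment estimate varies less from trial to trial than an analysis ignoring the strata assumes. The model standard error is then slightly too large, the Wald test rejects less often than 5% under the null, and some power is given up. Randomizing within groups and then not analysing by them discards part of what the design bought.

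A second issue concerns imputation. The Power section expects 80 of 100 participants per arm to be analyzable, so a meaningful share of outcomes may be imputed. If school status predicts both missingness and abstinence, leaving it out of the imputation model makes missing-at-random harder to defend.

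**Working it through.** **Inputs from the SAP.** Allocation 1:1:1 in blocks of 6 within school-status strata; 100 per arm with 80 analyzable; 25% (P+BC) versus 50% (V+BC); two-sided alpha 0.05; z-test on the logistic coefficient.

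**Assumed, because the SAP does not give them.** The split of school status (equal, or 25/75) and its odds ratio for abstinence (1 to 5).

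**Step 1: the plan's own figure.** For n = 80 per arm, difference d = 0.25 and mean rate 0.375:

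- Null SE = √(2 × 0.375 × 0.625 / 80) = 0.0765
- Alternative SE = √((0.25 × 0.75 + 0.50 × 0.50) / 80) = 0.0740
- Without continuity correction: Φ((0.25 − 1.96 × 0.0765) / 0.0740) = 0.912
- With continuity correction, d reduced by 1/80 = 0.0125: Φ((0.2375 − 1.96 × 0.0765) / 0.0740) = 0.882
- Fisher's exact test: 0.883

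The stated 0.88 therefore reproduces. The simulated powers below start near 0.91 because the logistic Wald test carries no continuity correction.

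**Step 2: size of the test without the stratum, large-sample formula.** Let r be the within-stratum outcome variance divided by the total variance. With arms balanced within strata, the actual size is 2 × (1 − Φ(1.96 / √r)). Example with equal strata, a 25% overall rate and odds ratio 3: the stratum rates are 0.151 and 0.349, so

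r = ½ × (0.151 × 0.849 + 0.349 × 0.651) / (0.25 × 0.75) = 0.948, and size = 0.044.

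The same formula gives 0.049 at odds ratio 1.5, 0.048 at 2 and 0.039 at 5.

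**Step 3: simulation.** 80 per arm, arms exactly balanced within two equal strata, overall rates held at 25%/50% (25%/25% for type I error), 40,000 trials per cell:

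| Stratum odds ratio | Type I error, without / with | Power, without / with | Gain (points) |
|---|---|---|---|
| 1 | 0.049 / 0.049 | – | – |
| 2 | 0.045 / 0.048 | 0.917 / 0.923 | 0.6 |
| 3 | 0.042 / 0.049 | 0.918 / 0.930 | 1.2 |
| 5 | 0.038 / 0.051 | 0.926 / 0.944 | 1.8 |

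A 25/75 split gives gains of 0.6, 1.1 and 1.7 points. With 100 per arm and equal strata the gains are 0.2 to 1.0 points. A separate simulation with actual permuted blocks (20,000 trials per cell; 30% or 50% in one stratum) gives losses of about 0.5, 1 and 2 points at odds ratios 2, 3 and 5, and essentially none at 1.

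**Step 4: closer to the plan.** 300 randomized in blocks of 6 within two equal strata, EUC excluded, 20% missing completely at random, complete cases, sex (no effect) and ECDI (assumed log odds ratio −0.3 per SD) in both models, 12,000 trials per cell:

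| Stratum odds ratio | Type I error, without / with | Power gain (points) |
|---|---|---|
| 2 | 0.051 / 0.052 | 0.4 |
| 3 | 0.044 / 0.050 | 0.9 |
| 5 | 0.041 / 0.051 | 1.9 |

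The Monte Carlo error of the type I figures is about 0.002.

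**Step 5: imputation illustration.** Assume odds ratio 3, equal strata, and 30% missing in one stratum against 10% in the other. Imputation within arm that ignores school status reproduces the arm's observed rate. For placebo, with the lower-abstinence stratum missing more:

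(0.7 × 0.1514 + 0.9 × 0.3486) / 1.6 = 26.23%; with the pattern reversed, 23.77%.

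For varenicline (stratum rates 0.3660 and 0.6340) the two values are 51.67% and 48.33%. Against a true difference of 25 points:

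- Same pattern in both arms: 51.67 − 26.23 = 25.4, or 48.33 − 23.77 = 24.6
- Opposite pattern by arm: 51.67 − 23.77 = 27.9, or 48.33 − 26.23 = 22.1

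This assumes that arm is used in the imputation and that all four weeks are missing. Observed weeks would shrink the shift.

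**The case against.** Leaving a stratification factor out of the model is valid, and the SAP is not wrong in any statement here. Nothing in it shows that school status predicts abstinence. At an odds ratio of 1.5 with ECDI in both models, power is 0.920 without and 0.922 with the term, and type I error is 0.050 versus 0.052, so there is nothing to notice. In the run closest to the plan, conservatism is not visible at odds ratio 2 either. Power exceeds 0.88 in every case examined. All of this stands, and it limits the point to a small, conditional gain.

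The imputation example is also fairly criticised. The plan imputes from a participant's other visits, which would carry much of any school-status effect, and the opposite-by-arm pattern is an extreme that no part of the SAP suggests. With the same pattern in both arms the shift is under half a point. The example shows that the direction is unknown; it is not an estimate of likely bias.

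For the inventory models no size was computed, and the baseline inventory score may already absorb part of any effect.

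The wording that sets two covariates as a minimum does permit adding school status. It does not name it, and the model sections then fix the terms to sex and ECDI. That is weaker than prespecification, because it leaves the choice of a primary-model term open.

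**Conclusion.** The point holds as a minor improvement. School status is used to randomize and then appears in no specified analysis, imputation or sensitivity model. If it is prognostic with an odds ratio of 2 to 5, the omission costs about 0.4 to 1.9 points of power, and the primary test runs at or somewhat below its nominal level (0.038 to 0.051 across the runs in steps 3 and 4). If it is not prognostic, nothing is lost. Type I error is not inflated, and the sample size and the stated power of 0.88 need no change. These figures rest on an assumed split and strength of school status. The effect would be smaller if ECDI or sex carried part of it. The simulations did not include multiple imputation, so they indicate size only.

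**What to change.** Name school status (secondary versus post-secondary, as randomized) as a covariate in the primary and secondary logistic models, in the GEE models for the inventories, and in every MICE model, or state why it is left out. Keep the planned run without covariates as the sensitivity analysis. The change should be made before treatment codes are opened.

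The cost is a few words in the SAP and one degree of freedom per model. No new data are needed, because school status must be known for each participant before randomization.

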2. **[P+BC arm]**. Participants will receive placebo tablets, identical in appearance to varenicline, up to 1 mg BID for 12 weeks. Additionally, participants will (a) attend the QuitVaping behavioral support sessions once per week for 12 weeks, and (b) be encouraged to sign up for the TIQ program. We plan to assign up to 100 participants to this arm.
3. **[EUC arm]** Participants will be assigned to a single-blind monitoring only group and will receive no drugs nor attend behavioral support sessions. Participants will receive a brief encouragement to enroll in the TIQ program. We plan to assign up to 100 participants to this arm.

All participants will have weekly assessments to monitor vaping behavior, will receive advice to quit vaping at the first post-baseline weekly visit and be referred to the TIQ vaping cessation app. Other study-related outcomes will be assessed at the monthly visits (weeks 4, 8, 12, 16, 20, and 24).

Participants

We will recruit nicotine dependent adolescents who vape, do not smoke regularly, and are willing to try treatment to stop vaping. To do so, we plan to enroll up to 300 adolescents (and randomize as many as possible) in Greater Boston meeting these criteria. Our inclusion criteria are:

- Ages 16-25 (inclusive);
- Self-report of daily or near daily nicotine vaping for the prior ≥ 3 months, bio-verified by saliva cotinine >30 ng/ml.
- Nicotine dependence as defined by a score ≥ 4 on the 10-item E-cigarette Dependence Inventory (ECDI), and/or report persistent use despite negative consequences or prior failed quit attempts;
- Self-report of no regular combusted tobacco use in the past 2 months at enrollment and exhaled CO <10 ppm;
- Total body weight at enrollment ≥ 35 kg (77 lbs);
- Are competent and able to consent (if 18 or older), or have a parent or legal guardian who is able and willing to provide written informed consent (if under the age of 18);
- Able to understand study procedures and read and write in English;
- For participants who could become pregnant: negative urine pregnancy test at enrollment and agree to use effective contraception (e.g., abstinence, hormonal contraception, intra-uterine device, sterilization, or double barrier contraception) during the study.

Our exclusion criteria are:

- Use of a smoking cessation medication in the prior month (nicotine patch, gum, nasal spray, or inhaler, varenicline, bupropion);

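### Baseline cotinine, already measured before randomisation, is not named in the abstinence models or their imputation; adding it would be a small, optional gain in power if it is prognostic

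*SAP*

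**What the plan says.** **Models.** For the primary outcome (Statistical Model and Tests): "The logistic regression model will include the 2 covariates assessed at baseline (biological sex and summed scores for the ECDI". The same sentence governs the secondary abstinence models (Secondary Outcomes, Biochemically-Verified Vaping Abstinence).

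**Imputation.** For the primary outcome (Missing Data): "Abstinence status will be imputed all non-missing time points and using the set of 2 covariates collected at the baseline visit described above". The secondary abstinence outcomes are imputed "via the same approach and covariates described for the primary outcome".

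**Covariate list.** The Covariates section is looser than the model sections: "We will use, at a minimum, 2 covariates in our analysis and missing data imputation". It then lists only sex and the ECDI sum.

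**Cotinine before randomisation.** Eligibility requires recent vaping "bio-verified by saliva cotinine >30 ng/ml" (Participants). The primary outcome's time-frame item adds "Self-reported abstinence and urine or saliva samples will be collected during (a) the baseline visit". Treatment is assigned to eligible participants who attend the baseline visit (Randomization), so both readings precede assignment.

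**Cotinine in the endpoint.** Self-reported abstinence is "verified given a semi-quantitative cotinine of less than 30ng/ml".

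**Power.** The stated design, "with 80 analyzable per arm, would yield power of 0.88 with a two-sided alpha of 0.05", takes abstinence of 25% in P+BC and 50% in V+BC. It mentions no covariate adjustment.

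**The concern.** The inventory models adjust for each participant's own baseline score on the inventory, and the inventory imputation uses that score too. The abstinence models have no counterpart. Baseline abstinence hardly varies, because everyone vapes at entry, so cotinine level is the nearest baseline measure of the biomarker that verifies the endpoint. ECDI, the only severity measure in the model, is a questionnaire.

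Heavier exposure at baseline could plausibly predict failure to reach and hold a cotinine below 30 ng/ml. If so, a model without it estimates a treatment odds ratio closer to 1 than the model that conditions on it, and the V+BC versus P+BC test has somewhat less power than the collected data allow.

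The open wording of the covariate list does not settle this. It names no further variable and no rule for choosing one, and the model sections specify two. A covariate named before unblinding is beyond challenge; one added afterwards is not.

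**Working it through.** **1. The plan's own power figure.** Inputs from Power: 80 per arm, 25% versus 50%, two-sided 0.05. The mean rate is 0.375.

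- SE under the null = √(2 × 0.375 × 0.625 / 80) = 0.0765
- SE under the alternative = √((0.25 × 0.75 + 0.50 × 0.50) / 80) = 0.0740
- With continuity correction: Φ[(0.25 − 1/80 − 1.96 × 0.0765) / 0.0740] = 0.882
- Exact power of Fisher's test: 0.883
- Without correction: 0.912

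The stated 0.88 therefore reproduces with the continuity-corrected and Fisher versions, and it does not involve cotinine. The simulations below use the planned z-test from a logistic model, which is uncorrected, so they start near 0.91.

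**2. Simulated power with and without cotinine.** From the SAP: 80 per arm, marginal abstinence 25% and 50%, sex and ECDI in the model. Assumed, because the SAP gives no values:

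- odds ratio for failure per SD of cotinine of 1.0 to 2.0, net of sex and ECDI
- ECDI slope of 0.3 log-odds per SD
- correlation of cotinine with ECDI of 0 or 0.4
- cotinine entered either as a numeric value or in four bands

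Outcome data are complete, with 4,000 trials per setting. Each cell gives power without → with cotinine.

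| OR per SD | Numeric, corr. 0 | Four bands, corr. 0 | Numeric, corr. 0.4 | Four bands, corr. 0.4 |
|---|---|---|---|---|
| 1.0 | 0.9197 → 0.9185 | 0.9123 → 0.9107 | 0.9020 → 0.9010 | 0.9147 → 0.9165 |
| 1.25 | 0.9135 → 0.9130 | 0.9115 → 0.9143 | 0.9225 → 0.9247 | 0.9160 → 0.9185 |
| 1.5 | 0.9143 → 0.9210 | 0.9097 → 0.9147 | 0.9240 → 0.9280 | 0.9270 → 0.9303 |
| 2.0 | 0.9123 → 0.9307 | 0.9087 → 0.9237 | 0.9267 → 0.9450 | 0.9217 → 0.9407 |

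The changes in percentage points are −0.16 to +0.18 at OR 1.0, −0.05 to +0.28 at 1.25, +0.33 to +0.67 at 1.5, and +1.50 to +1.90 at 2.0.

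A second set of runs, also at 80 per arm with sex and ECDI in the model, gave −0.3 to +0.1, about 0 to 1, 0.7 to 1.5, and 1.6 to 2.7 points. The Monte Carlo error of one power value at 4,000 trials is √(0.92 × 0.08 / 4000) = 0.4 points. The difference between two models fitted to the same trials is better determined than that. The sets agree that the gain is small, and differences of a few tenths of a point should not be read closely.

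**3. Where the gain comes from.** Mean estimate and mean SE of the treatment log odds ratio (numeric cotinine, correlation 0):

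| OR per SD | Without: estimate / SE = ratio | With: estimate / SE = ratio |
|---|---|---|
| 1.0 | 1.1659 / 0.3553 = 3.28 | 1.1730 / 0.3579 = 3.28 |
| 1.25 | 1.1523 / 0.3550 = 3.25 | 1.1733 / 0.3602 = 3.26 |
| 1.5 | 1.1564 / 0.3548 = 3.26 | 1.2078 / 0.3655 = 3.30 |
| 2.0 | 1.1477 / 0.3543 = 3.24 | 1.2774 / 0.3797 = 3.36 |

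The SE rises in every row. The estimate rises slightly faster when cotinine is prognostic. As a check, Φ(ratio − 1.96) goes from 0.900 to 0.920 at OR 2.0 (+2.0 points) and from 0.903 to 0.911 at OR 1.5 (+0.8), in line with the simulated gains.

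**4. Room for one more term.** Expected successes are 80 × 0.25 + 80 × 0.50 = 60. Arm, sex, ECDI and cotinine make four terms, or 15 successes per term.

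**The case against.** The strongest reply is that nothing here is an error. Sex and a baseline dependence score are prespecified, randomisation makes the comparison valid without cotinine, and a third covariate is a preference. As far as error goes, that stands: the point is an improvement on offer and no more.

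Several stronger readings are tempting, and the SAP does not support them:

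- **That the plan gives up precision or biases the treatment effect.** In logistic regression the SE of the treatment log odds ratio rises when a prognostic covariate is added. The smaller odds ratio without it is a different, less conditional estimand, not a biased one.
- **That the 0.88 is wrong.** It reproduces without any covariate.
- **That the gain is large.** With 25% versus 45%, runs at OR 2.5 per SD go from 76.1% to 81.9%. The SAP plans for 25% versus 50%, and it supplies no association between cotinine and abstinence, let alone one that strong.
- **That imputation would clearly improve.** Imputation already draws on abstinence at the other visits. No added value of cotinine beyond that was calculated.
- **That a suitable value certainly exists.** The reading is described as semi-quantitative, the baseline sample may be urine or saliva, and the entry rule truncates the range at 30 ng/ml. The SAP does not say that a graded result is kept.

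The parallel with the inventory models is also imperfect. They adjust for the baseline value of the outcome itself, whereas cotinine level is only related to abstinence status, which rests on self-report as well.

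One part of the reply does not hold. The open covariate list does not bring cotinine in, because the model and imputation sections specify two variables and name them.

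**Conclusion.** The point holds as a small, optional gain in power. Cotinine is measured in every participant before randomisation, yet the abstinence models and their imputation name only sex and ECDI. There is no bias and no wrong figure.

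Across both sets of runs at 80 per arm, adding it is worth about 0 to 1 point of power at an odds ratio of 1.25 per SD, roughly 0.3 to 1.5 points at 1.5, and about 1.5 to 2.7 points at 2.0. With no prognostic value the change stays within about 0.3 points of zero.

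These figures assume a prognostic strength net of sex and ECDI that the SAP does not give, complete outcome data, and a graded reading on one matrix. If only a result above or below 30 ng/ml is kept, the entry rule makes it the same for everyone and there is nothing to add.

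**What to change.** Before unblinding:

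1. Close the list in Covariates, so that it no longer sets only a floor and agrees with the model and imputation sections.
2. State whether a graded pre-randomisation saliva cotinine is recorded for all participants. The entry test is the natural source, since it is required of everyone and is specified in saliva.
3. If it is, add it as an ordered semi-quantitative level, or as the log value if numeric. Do not mix urine and saliva readings. Keep sex and ECDI.
4. Carry it into the logistic models for all three abstinence outcomes and into their MICE models. Say that it applies to abstinence only, because the inventory imputation refers back to the same two-covariate set. Update the first item in Sensitivity Analyses, which reruns the models without covariates.
5. If no graded reading exists, close the list at sex and ECDI.

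The cost is a few lines of SAP text and one more model term. If the reading is already recorded, no new samples or participants are needed. The covariate would be coarse and truncated at 30 ng/ml, which limits what it can add.
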